9.2 SAMPLE SIZE DETERMINATION

While studies on the effects of continuous theta-burst stimulation (cTBS) on critical dynamics have never been conducted, power calculations are based on prior work showing that cTBS can alter E/I balance and working memory function. Specifically, Schicktanz et al. (2015) found that a single train of cTBS to the left dorsolateral prefrontal cortex reduced N-back task accuracy (the same working memory task we will use in the present study) with an effect size on accuracy of $d = 1.39$, 3–21 minutes post-stimulation. This performance effect was established for the 2-back which is our mid-difficulty level. Using g*Power (Faul et al., 2007), we estimate that if the true effect size remains the same, we will have a 95% chance of detecting a cTBS effect on 2-back performance with 30 participants at $p < 0.05$. Importantly, with 30 participants, we will still have 80% power to detect a group difference in performance even if the true

effect size is less than half as large ($d = 0.53$). As such, our target recruitment is set at 30 participants (but will run additional to reach 30 complete participant-session sets, as needed, due to drop-out).

While effect sizes can vary in cTBS owing to considerable inter-individual differences in response to stimulation, we are taking additional measures to reduce reliability including participant-specific brain images and neuronavigation, and also the use of two, rather than one train of cTBS. As such, if anything, we expect the prior estimates to be a lower bound on what we observe.

While this estimate is based on working memory performance alone, this outcome is arguably the most important because it is the one measure that has been linked with E/I balance, with subjective effort, and with critical dynamics in other studies. As such, this measure was selected because it is also informative about all primary and secondary outcomes.

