9.4 STATISTICAL ANALYSES

9.4.1 GENERAL APPROACH

There are no categorical outcomes. Key measures are all continuous outcomes, and are described in detail in the next section. They will be analyzed according to pre- versus post-stimulation means. We will also report standard errors for each outcome. Key outcomes have multiple associated measures. Multiple measures will be used to assess reliability by parallel forms.

We will use standard frequentist cut-offs of $p < 0.05$ for all statistical tests, correcting for multiple comparisons. Key t-tests will include pre-post distinctions in E/I balance measures, working memory performance measures, and measures of criticality.

Covariates of no interest to be included are sex and age which we will incorporate via multiple regression to ask whether cTBS alters key outcomes (described in the next session).

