9.4.3 ANALYSIS OF THE SECONDARY ENDPOINT(S)

Secondary endpoints will be inter-correlations among the primary endpoint measures. Namely, these correlations will test whether the degree to which cTBS alters one measure correlates with stimulation effects on other measures. Given the large number of possible correlations, we will only test for correlations among those measures which show a reliable stimulation effect in the first place. We will then correct for multiple comparisons among these correlations by the false discovery rate method to control for Type I errors, limiting them to no more than 5% chance.

We will use Pearson's correlations for all tests since our outcome measures are continuous, interval measures.

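### Section 9.2's two power figures for 30 participants (95% at d = 1.39, 80% at d = 0.53) cannot come from one design, and the 80% is for a single test without the correction required in 9.4.1

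*Protocol*

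**What the plan says.** Protocol section 9.2 takes d = 1.39 for 2-back accuracy from an earlier single-train study and states that "we will have a 95% chance of detecting a cTBS effect on 2-back performance with 30 participants" at p < 0.05. It continues: "with 30 participants, we will still have 80% power to detect a group difference in performance even if the true" effect is d = 0.53. The recruitment target follows at once: "As such, our target recruitment is set at 30 participants", with extra recruitment to reach 30 complete sets. The section admits its narrow base ("While this estimate is based on working memory performance alone"). It names G*Power but gives no test, no sidedness and no scale for d.

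Other sections that bear on these figures:

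- Sections 4.1 and 9.3 describe a within-participant design in which each person is their own control.
- Section 9.4.1 sets p < 0.05 "for all statistical tests, correcting for multiple comparisons", with no method and no family. It adds: "Key t-tests will include pre-post distinctions in E/I balance measures, working memory performance measures, and measures of criticality".
- Section 3 and the regression in 9.4.2 compare stimulation sites, not pre with post.
- Section 9.4.3 names a method, but only for the secondary correlations: "We will then correct for multiple comparisons among these correlations by the false discovery rate method".
- Section 9 states that there will be no formal SAP.

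**The concern.** The two effects differ by a factor of 1.39 / 0.53 = 2.62, yet power is said to rise only from 80% to 95%. Power climbs much faster than that with effect size at a fixed N, so the pair looks like output from two different calculations. Calling the contrast a group difference, in a trial with no parallel groups, adds to the doubt.

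The second figure matters more, because it sets the sample size. It is quoted at p < 0.05 for one outcome, while 9.4.1 promises a corrected threshold for every test. If the 2-back test belongs to the corrected family, its power at d = 0.53 is not 80%. With no SAP to follow, a reader cannot find out which applies.

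**Working it through.** **Inputs.** From 9.2: N = 30 complete sets, p < 0.05, d = 1.39 with 95%, d = 0.53 with 80%. From 4.1 and 9.3: within-participant design. Sidedness and the scale of d are not given, so alternatives are tried.

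**Formulas** (exact noncentral t).
- Paired: noncentrality = dz × √N, df = N − 1.
- Independent groups, n per group: noncentrality = d × √(n/2), df = 2n − 2.
- If d is on the raw-SD scale: dz = d / √(2(1 − r)), where r is the within-person correlation.

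**Step 1: the 80%.** Paired, two-sided, df 29, critical t = 2.045. Noncentrality = 0.53 × √30 = 2.903, and power = 80.1%. The stated figure reproduces.

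**Step 2: the 95% in the same design.** Noncentrality = 1.39 × √30 = 7.613, and power exceeds 99.99%. The stated figure does not reproduce. In this design 95% is reached at dz = 0.681, against 0.529 for 80%: a ratio of 1.29 (one-sided 0.615 / 0.465 = 1.32). The plan's ratio is 2.62.

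**Step 3: other designs, alpha 0.05.**

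| Design | Power at 1.39 | Power at 0.53 |
|---|---|---|
| As stated | 95% | 80% |
| 30 pairs, two-sided | >99.99% | 80.1% |
| 30 pairs, one-sided | >99.99% | 88.3% |
| 15 v 15, two-sided | 95.7% | 28.9% |
| 15 v 15, one-sided | 98.1% | 41.0% |
| 30 v 30, two-sided | 99.96% | 52.3% |
| 30 v 30, one-sided | 99.99% | 64.9% |

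No row gives the pair. The 95% comes close to 15 v 15 (noncentrality 1.39 × √7.5 = 3.807, df 28), and the 80% fits 30 pairs. That may explain the mismatch, but the document does not say so.

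**Step 4: d on the raw-SD scale** (30 pairs, two-sided; r is assumed, since none is given).

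| r | dz for 0.53 | Power at 0.53 | Power at 1.39 |
|---|---|---|---|
| 0.3 | 0.448 | 66.0% | >99.9% |
| 0.5 | 0.530 | 80.1% | >99.99% |
| 0.7 | 0.684 | 95.2% | >99.99% |

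Extending r to −0.5 gives 98.9% at 1.39 and 36.7% at 0.53. No correlation tried, from −0.5 to 0.9, restores the pair.

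**Step 5: effect of the 9.4.1 correction at dz = 0.53.** The plan names no method for the primary tests, so Bonferroni is an illustration. The families are also assumed: 3 (primary domains in the synopsis) and 4 (domains in 9.4.2).

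| Tests | Two-sided power | One-sided power | dz for 80%, two-sided |
|---|---|---|---|
| 1 | 80.1% | 88.3% | 0.529 |
| 3 | 64.2% | 74.6% | 0.622 |
| 4 | 59.8% | 70.4% | 0.645 |

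On the raw-SD scale, r = 0.3 / 0.5 / 0.7 gives 48% / 64% / 88% for 3 tests and 43% / 60% / 85% for 4. Losing one df for session order (df 28) gives 80.0%, 64.0% and 59.6% for 1, 3 and 4 tests, so that covariate does not explain anything.

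Benjamini-Hochberg, by simulation (two-sided, 30 pairs, 3 or 4 outcomes, correlation between outcomes 0 or 0.5), gives the 2-back test about 75–78% if every outcome has dz = 0.53, and about 60–65% if the others are null.

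**The case against.** The best defence is that nothing turns on the 95%. It understates power for the planned design, would be true if read as at least 95%, and correcting it changes neither the sample size nor any test. The figure that does set the sample size is right to a tenth of a point for a two-sided paired test, which is the natural reading of a within-participant trial. Section 9.2 says openly that it rests on one outcome, and quoting power for a single test at nominal 0.05 is common. Bonferroni is not in the protocol. Under a false discovery rate method with effects in every domain, as the protocol predicts, the loss is only a few points.

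Much of this stands. The error is conservative, 30 is not shown to be too few, and the Bonferroni figures mark the pessimistic part of a range. Three things do not go away. The text gives 95% as the power, not as a floor. The 80% can be identified as a paired two-sided test on dz only by working backwards. And every two-sided corrected calculation at dz = 0.53 falls below 80%, including the favourable false discovery rate case. The pre-post versus site question and the unnamed primary correction are partly issues of their own; the arithmetic conclusion does not depend on them.

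**Conclusion.** The concern holds. The stated pair cannot come from one t-test design at 0.05, and 95% at d = 1.39 is wrong for 30 pairs, where power exceeds 99.99% on the dz scale. This stays above 99.9% on the raw-SD scale for assumed correlations of 0.3 to 0.7. The direction is conservative, so the mismatch itself does not weaken the case for 30.

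The 80% at 0.53 is correct for one two-sided paired test at uncorrected 0.05 with d read as dz. It does not carry over to a two-sided corrected analysis at that effect: about 60–64% under Bonferroni for 3 or 4 tests, and about 60–78% under Benjamini-Hochberg depending on the other outcomes. Those ranges rest on assumed methods and families, and on a different scale for d they would move with a correlation the protocol does not give. This should be fixed, but it does not threaten the trial's feasibility.

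**What to change.** Rewrite 9.2 for one design:

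1. State the test as a two-sided paired comparison of dlPFC with angular gyrus stimulation, N = 30, on one named 2-back measure, with the effect as dz. If 1.39 or 0.53 is on another scale, say so and give the assumed within-person correlation. Drop the group-difference wording, and align the working-memory contrast in 9.4.1 with section 3 and 9.4.2.
2. Replace 95% with more than 99% at dz = 1.39.
3. Say that 80% at dz = 0.53 is for a single test at uncorrected 0.05.
4. Name the correction method and family for the primary tests in 9.4.1, and give in 9.2 the dz detectable with 80% power under it: about 0.62 for 3 tests or 0.645 for 4 if Bonferroni is chosen.

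The alternative is to name the 2-back measure as the sole confirmatory test at 0.05, outside the corrected family. That must first be reconciled with 9.1, whose primary hypotheses leave out working memory, and with the several primary objectives in section 3.

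The cost is a text change with no added participants. The drawback is a less favourable stated power for the corrected analysis.

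### The 80% power at d = 0.53 in Protocol 9.2 is computed at an unadjusted 0.05, while 9.4.1 corrects all tests for multiplicity and exempts none

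*Protocol*

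**What the plan says.** Protocol 9.2 bases the sample size on N-back performance. It takes from an earlier study a result "with an effect size on accuracy of $d = 1.39" and gives the power for that effect "with 30 participants at $p < 0.05", with no mention of adjustment. It then offers a fallback at d = 0.53, under half of the earlier value, and states that "with 30 participants, we will still have 80% power to detect a group difference in performance even if the true" value falls to that level. Drop-outs are replaced, since the study "will run additional to reach 30 complete participant-session sets, as needed, due to drop-out", so 30 complete pairs is the right number to work with.

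Protocol 9.4.1 sets a 0.05 threshold "for all statistical tests, correcting for multiple comparisons". It lists working memory performance among the main t-tests, beside the E/I and criticality measures. Protocol 9.4.2 then lists four outcome domains with ten bulleted measures, three of them from the N-back.

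The protocol names no correction method for these tests. The false discovery rate in 9.4.3 is for the correlations between stimulation effects. Section 9 says that no formal SAP will be written.

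**The concern.** The sample size section and the analysis section use different significance levels for the same outcome. In 9.2, N-back performance is tested alone at 0.05. In 9.4.1 it is one of several tests that share a correction, and nothing takes it out. Section 9.2 calls working memory arguably the most important outcome, but that description does not rank it first in a testing order or set alpha aside for it.

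The fallback at d = 0.53 is what tells a reader that the trial remains informative if the earlier effect proves much too large. Someone interpreting a non-significant N-back result would rely on it. If the test is in fact run at a smaller alpha, that reader credits the trial with more sensitivity than it has. Because the protocol expects no SAP, no later document is due to settle the matter.

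**Working it through.** **Inputs.** n = 30 complete pairs, d = 0.53, alpha = 0.05 and stated power 80% (all Protocol 9.2); within-subject design (4.1); correction of all tests (9.4.1). Sidedness, the size of the family and the correction method are not stated.

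**Step 1: reproduce the plan's figure.** For a paired t-test, df = n − 1 = 29 and the noncentrality is d × √n = 0.53 × √30 = 2.903. Two-sided power at level α is P(T > t_crit), where T is noncentral t and t_crit is the 1 − α/2 quantile of t with 29 df; the opposite tail is negligible. At α = 0.05, t_crit = 2.045 and power is 80.1%.

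Other readings at d = 0.53 do not give 80%:
- paired, one-sided 0.05: 88.3%
- independent groups of 15 and 15, two-sided: 28.9%
- independent groups of 30 and 30, two-sided: 52.3%

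So the 80% is a single paired two-sided test at an unadjusted 0.05. The smallest d with 80% power under that test is 0.529, so no slack is left to absorb a correction.

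**Step 2: apply a correction.** Same formula with α = 0.05/m (Bonferroni). The number of tests m is my assumption.

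| m | α | t_crit | Power at d = 0.53 | d with 80% power |
|---|---|---|---|---|
| 1 | 0.0500 | 2.045 | 80.1% | 0.529 |
| 2 | 0.0250 | 2.364 | 70.4% | 0.589 |
| 3 | 0.0167 | 2.541 | 64.2% | 0.622 |
| 4 | 0.0125 | 2.663 | 59.8% | 0.645 |
| 10 | 0.0050 | 3.038 | 46.0% | 0.715 |

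Four is the number of domains in 9.4.2, ten the number of bulleted measures there, and three the number of primary objectives in Section 3. Two would fit the two N-back endpoints in Section 3, discrimination accuracy and reaction time.

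**Step 3: less strict methods.** Simulation with four independent outcomes, n = 30, 40,000 runs:
- Holm: about 60% if only the N-back effect is real, about 72% if all four have d = 0.53.
- Benjamini-Hochberg: about 60% and about 77% in the same two cases.

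**Step 4: the planning effect.** At d = 1.39 the noncentrality is 1.39 × √30 = 7.61, against a critical value of 3.038 even for ten tests. Paired power stays above 99.9%. At half that effect, d = 0.695, power is 86% with four Bonferroni-corrected tests and 77% with ten.

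**The case against.** The strongest reply is that nothing in 9.2 is miscalculated. The 80% is right at the alpha given there, the section admits that it considers working memory alone, and d = 0.53 is only the fallback. The lead figure uses d = 1.39, where correction is irrelevant, and at half that effect 30 participants still give over 80% power with four corrected tests. All of this stands, and it limits the point to the d = 0.53 statement. It does not remove the conflict, because 9.4.1 brings the same outcome under the correction.

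Four stronger readings are tempting, and the documents do not support them:

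- **That any correction would break the claim.** A fixed sequence with the 2-back first would keep the full 0.05, and a one-sided test shared between two comparisons would also give 80.1%. The protocol adopts neither, but neither is ruled out in principle.
- **That the family has sixteen members.** That count needs bullets in 9.4.2 to be split into single ratings, trial types and exponents. Section 9.4.1 also gives multiple measures of one outcome a reliability role, which argues for fewer confirmatory tests.
- **That a null result would be a coin flip.** This picks one point from a range running from 46% to 77% under the assumptions above.
- **That the remark "if anything, we expect the prior estimates to be a lower bound on what we observe" makes the shortfall worse because the control site is also stimulated.** Section 6.1.1 does expect cTBS to act at diverse sites, but it also argues that the angular gyrus is minimally coupled to working memory networks. The earlier study's comparator is not in the documents. In any case this concerns the effect size, not alpha.

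**Conclusion.** The point holds for the d = 0.53 statement. The 80% belongs to an unadjusted test, and the analysis rule as written does not run that test. With four outcomes, power is about 60% under Bonferroni and 60% to 77% under Holm or Benjamini-Hochberg. Across Bonferroni families of two to ten it runs from 70% down to 46%.

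These figures assume a two-sided paired t-test, which is the only version tried that matches the stated 80%. The simulations also assume independent outcomes. The regression on sex and age in 9.4.2 is not modelled. The size of the loss should be quoted as a range, since the protocol fixes neither family nor method. The documents do not support concluding that 30 participants are too few for the planning effect.

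**What to change.** Choose one of two routes before results are seen.

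(a) In 9.2 and 9.4.1, name one 2-back accuracy measure as the single sizing outcome, tested first at two-sided 0.05 outside the corrected family, and keep the 80% figure. This means choosing between the accuracy rate and d', both listed in 9.4.2. Section 9.4.1 should also say whether the remaining tests depend on this one. If they are run regardless, with their own 5% family error rate, the overall error can reach 5% + 5% = 10%.

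(b) In 9.4.1, fix which tests form the family and which correction applies, and restate the power in 9.2 at that alpha. For example, four outcomes with Bonferroni would read 60% at d = 0.53 and 80% at d = 0.645.

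Both are changes of wording and need no added participants or procedures. The cost of (a) is committing to one measure in advance. The cost of (b) is a less favourable stated power.

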9.3 POPULATIONS FOR ANALYSES

All participants will be included in all analyses because we are using a within-participant design.

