4.4 END-OF-STUDY DEFINITION

A participant is considered to have completed the study if he or she has completed the MR scan session, one target stimulation session, and one control session.

The end of the study is defined as completion of the second stimulation session as shown in the Schedule of Activities (SoA), **Section 1.3**.

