5.5 STRATEGIES FOR RECRUITMENT AND RETENTION

Participants will be recruited via flyers and announcements which detail core inclusion / exclusion criteria. As such we only anticipate needing to recruit around 40 individuals in order to meet our target (30 participants; 15 male / 15 female) recruitment. Flyers will be posted around the Brown University Community, and announcements will be posted in local periodicals (e.g. the Today @ Brown newsletter), which is appropriate for communicating with a sample of young adults in the target age range. This recruitment strategy has proven successful in recruiting participants who match community demographics in prior study and we anticipate it will remain successful going forward.

Potential participants who see our flyers and announcements will be invited to expressing their interest by emailing us. We will respond to this email with a brief description of what is involved in the study and inclusion / exclusion criteria. Our email will also instruct potential participants to simply say that yes they do or do not meet all of the screening criteria (without specifying which criteria they do / do not meet). If they say they meet all criteria, they are invited to a first session for informed consent procedures. After they give consent, they then fill out detailed screening forms which we retain as part of the study record.

Our anticipated enrollment will approximate the demographics of Providence, Rhode Island and the Brown University community including 26 not Hispanic or Latino and 4 Hispanic or Latino participants. Racial breakdown will approximate 2 Asian, 2 Black or African American, 22 White, and 4 More than One Race participants. All participants will be between the ages of 18 and 45.

To increase the chances that participants come to all study sessions, we will describe the procedures in detail during the recruitment and consenting processes, indicating that we are recruiting participants who would be willing to participate in all sessions (though participants can, at any time, decide to no longer participate and there will be no penalty if that happens). We will also send participants a calendar invite to remind them of their participation and a reminder email the day before their session.

Participants will be paid \$20/hour for MRI, or TMS and EEG experiments. Depending on the experiment, participants may have the opportunity to earn additional compensation. Specifically, participants will have

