6.4 STUDY INTERVENTION/EXPERIMENTAL MANIPULATION ADHERENCE

Participation in all three sessions (MRI and two stimulation sessions) is mandatory for participants to remain active participants in the study. Participation will be tracked across sessions by a single ID number associated with all data collected across the three sessions. All study components will be completed within one of the three sessions, so there is no issue of adherence beyond those three sessions.

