7.2 PARTICIPANT DISCONTINUATION/WITHDRAWAL FROM THE STUDY

Participants are free to withdraw from participation in the study at any time upon request.

An investigator may discontinue a participant from the study for the following reasons:

- Identification of brain abnormalities during the MRI scan
- Non-compliance with regards to cognitive task instructions
- Lost-to-follow up; unable to contact subject (see **Section 7.3, Lost to Follow-Up**)
- Any event or medical condition or situation occurs such that continued collection of follow-up study data would not be in the best interest of the participant or might require an additional treatment that would confound the interpretation of the study; With TMS an unlikely but possible medical condition would be onset of a seizure
- The participant meets an exclusion criterion (either newly developed or not previously recognized) that precludes further study participation

The reason for participant discontinuation or withdrawal from the study will be recorded on the Case Report Form (CRF). Subjects who sign the informed consent form and are randomized but do not receive the study intervention may be replaced. Subjects who sign the informed consent form, and are randomized and receive the study intervention, and subsequently withdraw, or are discontinued from the study, will be replaced.

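### Section 9.3 does not settle who enters the dlPFC-versus-angular-gyrus contrast: everyone stimulated, or 30 completers left after replacement

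*Protocol*

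**What the plan says.** - **Analysis population (Section 9.3).** The whole section is one sentence: "All participants will be included in all analyses because we are using a within-participant design".
- **Replacement (Section 7.2).** Participants who are "randomized and receive the study intervention, and subsequently withdraw, or are discontinued from the study, will be replaced". For those who leave before stimulation the rule is only permissive: "randomized but do not receive the study intervention may be replaced".
- **Target (Section 9.2).** The trial aims for 30 and "will run additional to reach 30 complete participant-session sets, as needed, due to drop-out".
- **Staying in the study (Sections 6.4 and 4.4).** "Participation in all three sessions (MRI and two stimulation sessions) is mandatory for participants to remain active participants in the study". A completer is someone who has "completed the MR scan session, one target stimulation session, and one control session".
- **Analysis (Sections 9.4.1 and 9.4.2).** The key t-tests are pre-post comparisons. The primary models regress each outcome on stimulation condition, controlling for sex and age. No participant term is named.
- **No later document.** Section 9 opens by saying that there will be no formal SAP, so Section 9.3 is the only definition of the analysis set.

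**The concern.** A within-participant design gives no ground for saying that everyone can be analysed. For the dlPFC-versus-angular-gyrus contrast it makes one-session participants harder to include. Meanwhile the recruitment rules build a set of 30 complete pairs, and the protocol never says what happens to the data of those who were replaced. Two analysts could follow the text and produce different datasets, and the choice could be made after the results are seen.

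This matters because leaving may be linked to the effect under study. Section 7.1 lists discomfort as a reason to stop a session. Section 7.2 lets the investigator discontinue a participant for "Non-compliance with regards to cognitive task instructions", which lies close to the N-back and effort outcomes. Section 6.3 says the experimenter knows which site is being stimulated. If people with a larger dlPFC effect are more likely to leave, a comparison restricted to completers understates that effect.

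**Working it through.** **1. What the sample size counts.** Inputs from Section 9.2: n = 30, d = 0.53, p < 0.05 (taken as two-sided), power 80%. For a paired t-test the noncentrality is d√n = 0.53 × √30 = 2.90, with critical value 2.045 on 29 df. Power is 80.1%, so the stated figure is reproduced and the 30 are complete pairs.

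**2. What each analysis needs.**

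| Analysis | One session enough? |
|---|---|
| Pre-post t-tests (9.4.1) | Yes, both values come from the same session |
| Regression on condition (9.4.2) | Mechanically yes, one row per session, but with no participant term |
| Paired site contrast, as powered in 9.2 | No |

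**3. Cost of having no participant term.** Assume a between-session correlation of 0.5. The paired and unpaired standardised effects are then equal, because √(2(1 − 0.5)) = 1. Treating the 60 rows as independent gives an expected t of 0.53 × √15 = 2.05 against a critical value of 2.00. Power is about 53%, compared with 80% paired. Using 9.4.2 as written to admit one-session rows therefore gives up the pairing on which 9.2 relies.

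**4. Possible bias in a completer analysis.** The assumptions here are mine: personal effects with mean 0.53 and SD 1; 30 + k people stimulated; the k with the highest leaving score replaced; correlation r = 0.3 between that score and the personal effect. With p = k/(30 + k) and z the upper-p normal quantile, the downward shift is r × φ(z)/(1 − p):

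- k = 3: p = 3/33 = 0.091; 0.3 × 0.180 = 0.054; effect 0.53 − 0.054 = 0.48.
- k = 5: p = 5/35 = 0.143; 0.3 × 0.263 = 0.079; effect 0.53 − 0.079 = 0.45.

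Someone who leaves after an angular gyrus first session has had no dlPFC stimulation. If only the dlPFC-first half can leave because of the dlPFC effect, the shift halves: 0.53 − 0.027 = 0.50 and 0.53 − 0.040 = 0.49. Power is by simulation of the paired t-test on the 30 completers (40,000 trials per setting):

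| Replaced | All can leave for this reason | Only dlPFC-first can |
|---|---|---|
| 3 | 0.48, power 73% | 0.50, power 77% |
| 5 | 0.45, power 68% | 0.49, power 74% |

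At r = 0 the effect stays at 0.53 and power at 80%.

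**5. What a mixed model recovers.** Suppose 34 people are stimulated and the four lowest scorers after a first dlPFC session leave (between-session correlation again 0.5). The completer estimate is about 0.45. A mixed model that keeps the leavers' single session gives about 0.53, which is the truth. If leaving instead depends on the personal site difference, which is mostly unobserved, the gain is small: with five leavers and correlations of 0.5 to 0.8, the estimate moves only from 0.45 to between 0.46 and 0.47.

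**The case against.** The other side can fairly say that Section 9.3 is the only statement about analysis sets and that it includes everyone. Sections 7.2 and 9.2 are recruitment rules, and 9.2 speaks of running additional participants. Read together, they can mean: analyse all, and recruit until 30 are complete. Two of the three primary predictions in Section 9.1 are relative to pre-stimulation rest, for which one session is enough. All of this stands. What it leaves open is the site contrast, which carries the working-memory and effort objectives in Section 3 and the power calculation.

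A reader might go further and infer four stronger points. The documents do not support them:

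- **That the analysed set will be 30 completers.** No section says replaced participants' data are dropped. The text permits that reading but does not require it.
- **That the planned methods cannot use one-session data.** The pre-post tests can, and so, mechanically, can the 9.4.2 regression.
- **That losses would be hidden behind a constant 30.** Section 7.2 records reasons on the CRF, and Section 10.1.6 has disposition and reasons for drop-out reported. Only a breakdown by condition and session is missing.
- **That 10 stimulated participants would be lost.** Section 5.5 says "we only anticipate needing to recruit around 40 individuals in order to meet our target", but that figure does not separate screening losses from drop-out.

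Replacing leavers to protect power is also legitimate in itself.

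**Conclusion.** The point holds as an unresolved analysis population for the site contrast. It does not show that a biased analysis has been planned. It is certain from the text that the reason in 9.3 is wrong for a paired contrast, that replacement after stimulation is mandatory, and that the status of leavers' data is not stated. The size of any bias cannot be derived from the documents. Under the assumed r = 0.3 with 3 to 5 replaced, an effect of 0.53 would appear as about 0.45 to 0.50, with power about 68% to 77%. It would be unbiased if leaving is unrelated to the dlPFC effect. The correction should be made before data are analysed, since no SAP will follow to make it.

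**What to change.** - **Section 9.3:** define the primary set as every participant who received at least one stimulation session and has outcome data, and remove the present reason.
- **Section 9.4.2:** analyse the site contrast with a mixed model that uses one-session data: random participant; fixed condition and session order (Section 4.1 already promises session order in all analyses); sex and age as planned.
- **Sections 7.2 and 9.2:** state that replacements are added to the participants already stimulated and that leavers' data are kept.
- **Reporting:** give the analysis of the 30 complete sets as a sensitivity analysis, and tabulate withdrawals by condition, session and reason.
- **Limitation to state:** the mixed model corrects only for leaving that is explained by observed data.

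The cost is wording in four sections and a slightly more complex model. Recruitment to 30 complete sets is unchanged.
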